11.3 Vital Signs

Descriptive statistics for vital signs (systolic and diastolic blood pressures [sitting and standing], pulse rate [sitting and standing], respiratory rate, temperature, weight, orthostatic systolic blood pressure, orthostatic diastolic blood pressure, and orthostatic pulse rate) values at baseline, postbaseline, and changes from baseline values at each postbaseline timepoint will be presented by treatment group. Orthostatic vital sign values (orthostatic systolic and diastolic blood pressures, and orthostatic pulse rate) are defined as the corresponding standing measurement minus sitting measurement of systolic and diastolic blood pressures and pulse rate respectively.

Vital sign values will be considered PCS if they meet both the observed value criterion and the change from baseline value criterion, if both criteria are available, or meet either the observed value criterion or the change from baseline value criterion that will be detailed in Table 11-3. The number and percentage of participants who have PCS postbaseline vital sign values will be tabulated by treatment group. The percentages will be calculated relative to the number of participants who have available baseline or non-PCS baseline (for parameters with only the observed value criterion) values and at least 1 postbaseline assessment. The numerator will be the total number of participants with at least 1 PCS postbaseline value during the study. A supportive listing of participants with PCS postbaseline values will be provided. In addition, a tabular display showing all AEs that occurred in participants who had PCS postbaseline vital sign values will be provided.

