## 4 Study Population and Entry Criteria

# 4.1 Number of Participants

Approximately 700 participants will be randomized (5:2) to atogepant 60 mg QD (500 participants) or oral SOC migraine prevention medication (200 participants) at approximately 115 centers in the United States. A minimum of 200 participants randomized to atogepant must be classified as *De Novo* Participants (see definition below).

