9.2 Measurement of Treatment Compliance

Dosing compliance for a specified period is defined as the total number of open-label study medications actually taken by a participant during that period divided by the number of open-label study medications that were expected to be taken during the same period multiplied by 100. The total number of capsules actually taken during a specific period will be calculated

Allergan

SAP 3101-302-002 AGN-241689

from the study medication record. Descriptive statistics for open-label study medication dosing compliance together with the compliance categories (< 80%, 80% - 120%, > 120%) will be summarized only for the atogepant arm at each period between 2 consecutive visits, as well as during the whole open-label treatment period of the study for the Safety Population.

Allergan	SAP 3101-302-002 AGN-241689

Allergan

Allergan

Allergan

Allergan	 SAP 3101-302-002 AGN-241689

11 Safety Analyses

The safety analysis will be performed using the Safety Population. The safety parameters will include adverse events (AEs), clinical laboratory, vital sign, electrocardiographic (ECG), and C-SSRS. For clinical laboratory, vital sign, and ECG, the last nonmissing safety assessment before the first dose of treatment will be used as the baseline for all analyses of that safety parameter. Continuous variables will be summarized by number of participants and mean, SD, median, Q1, Q3, minimum, and maximum values. Categorical variables will be summarized by number and percentage of participants.

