11.2 Clinical Laboratory Assessments

Descriptive statistics for clinical laboratory values (in both SI and conventional units) at baseline, postbaseline, and changes from baseline values at each postbaseline timepoint will be presented by treatment group for the following laboratory parameters:

Allergan SAP 3101-302-002 AGN-241689

Hematology: Hemoglobin, hematocrit, red blood cell count, red blood cell

indices (mean corpuscular volume, mean corpuscular hemoglobin, mean corpuscular hemoglobin concentration), white blood cell count, including differential (neutrophils, lymphocytes, monocytes, eosinophils, and basophils),

platelet count

Chemistry: Sodium, potassium, chloride, bicarbonate, glucose, blood

urea nitrogen, creatinine, total bilirubin, alkaline phosphatase, aspartate aminotransferase, alanine

aminotransferase, lactate dehydrogenase, creatine kinase, total protein, albumin, calcium, phosphorus, uric acid, total

cholesterol

Urinalysis: Specific gravity, pH

In addition, descriptive statistics for values and changes from the baseline values in conventional units at each assessment time point will be presented for selected clinical laboratory parameters listed in Appendix I. A description of reporting the lab values in conventional units in patient narratives (along with the standard reporting in SI units) is presented at the end of Appendix I.

Clinical laboratory test values will be considered potentially clinically significant (PCS) if they meet either the lower-limit or higher-limit PCS criteria listed in Table 11-1. The normal range for eGFR was not specified by the lab. Therefore, eGFR<60 mL/min/1.73m² is defined in Table 11-1 to classify renal function as the category of "Moderate eGFR Decrease or Worse" based on FDA guidance on PK studies in patients with impaired renal function. The number and percentage of participants who have PCS postbaseline clinical laboratory values will be tabulated by treatment group. The percentages will be calculated relative to the number of participants with available non-PCS baseline values and at least 1 postbaseline assessment. The numerator will be the total number of participants with available non-PCS baseline values and at least 1 PCS postbaseline value during the study. A supportive tabular display of participants with PCS postbaseline values will be provided, including the PID number, baseline and all postbaseline (including non-PCS) values.

[figure not shown]

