11.4 Electrocardiograms

[figure not shown]
Descriptive statistics for ECG parameters (ie, heart rate, PR interval, QRS interval, RR interval, QT interval, and QTc interval) at baseline, postbaseline, and changes from baseline values at each postbaseline timepoint will be presented by treatment group.

ECG parameter values are considered PCS if ECG values meet either the actual value or change from baseline PCS high criteria listed in Table 11-4. The number and percentage of participants with PCS postbaseline values will be tabulated by treatment group. The percentages will be calculated relative to the number of participants with an available non-PCS baseline value and at least 1 postbaseline assessment. The numerator will be the total number of participants with an available non-PCS baseline value and at least 1 PCS postbaseline ECG value during the study. A supportive listing of participants with PCS postbaseline values will be provided. A listing of all AEs for participants with PCS ECG values will also be provided.

Table 11-4 Criteria for Potentially Clinically Significant Electrocardiograms

To evaluate ECG postbaseline values of clinical interest, the number and percentage of participants with post-treatment QTcF > 450 msec, > 480 msec, and > 500 msec will be tabulated by treatment group.

The number and percentage of participants with an increase > 30 msec but \le 60 msec, and with an increase > 60 msec in QTcF will be tabulated. Participants will be counted only once for the most severe category. A supportive listing of participants with postbaseline QTcF increases > 30 msec will be provided, including the PID number, study center, and all QTc values (including changes from baseline). A listing of all AEs for participants with postbaseline QTcF increases > 30 msec will also be provided.

A shift table from baseline to the end of open-label treatment period in the investigator's overall interpretation of the ECG will be presented by treatment group for the following categories: normal; abnormal, not clinically significant; abnormal, clinically significant. A tabular display of participants with postbaseline clinically significant ECG abnormalities according to the investigator's overall interpretation will be provided.

[figure not shown]

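### The vital-sign PCS percentage counts participants already PCS at baseline in its numerator but excludes them from its denominator

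*SAP*

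**What the plan says.** SAP 11.3 classes a vital-sign value as PCS when it meets both an observed value criterion and a change from baseline criterion, if both exist. Where only one exists, the value must "meet either the observed value criterion or the change from baseline value criterion that will be detailed in Table 11-3".

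For the percentages, the base is "relative to the number of participants who have available baseline or non-PCS baseline (for parameters with only the observed value criterion) values"; one or more postbaseline assessments are also required. The next sentence defines the numerator: "The numerator will be the total number of participants with at least 1 PCS postbaseline value during the study". It says nothing about baseline status.

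The two parallel rules are worded differently:

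- **Laboratory (SAP 11.2):** "The numerator will be the total number of participants with available non-PCS baseline values and at least 1 PCS postbaseline value during the study". The denominator carries the same non-PCS baseline condition.
- **ECG (SAP 11.4):** "The numerator will be the total number of participants with an available non-PCS baseline value and at least 1 PCS postbaseline ECG value". The denominator again carries the same condition.

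Baseline is defined once for all three data types in the opening paragraph of SAP Section 11: "the last nonmissing safety assessment before the first dose of treatment will be used as the baseline for all analyses of that safety parameter".

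**The concern.** When a parameter has only an observed value criterion, a baseline value can itself be PCS. SAP 11.3 removes such participants from the denominator, which is the usual way to describe abnormality that emerges on treatment. It does not remove them from the numerator. Anyone PCS at baseline and again later is counted as a case without being counted as at risk. So is anyone with no baseline value who has a PCS value later.

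The table would then mix abnormality present before the first dose with abnormality that appeared after it. Safety and tolerability is the only stated objective (Protocol 2.1, SAP Section 5), and Protocol 3.1 gives comparative safety data as the purpose of the standard-of-care arm. The percentage is shown by treatment group, so a chance difference between arms in recurring baseline abnormality would look like a treatment difference.

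**Working it through.** The documents give no vital-sign PCS percentage, so there is no planned figure to reproduce. The check compares the two sets and then illustrates the size.

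**Is the baseline condition on both sides?**

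| Rule | Denominator requires non-PCS baseline | Numerator requires non-PCS baseline |
|---|---|---|
| Laboratory PCS, SAP 11.2 | yes | yes |
| Hepatic abnormalities, SAP 11.2 | no | no |
| ECG PCS, SAP 11.4 | yes | yes |
| Vital-sign PCS, observed value only, SAP 11.3 | yes | **no** |

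Only the vital-sign pair does not match.

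**Formula.** For one observed-value-only parameter, let:

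- N = participants with baseline and postbaseline data
- B = those PCS at baseline
- a = those newly PCS among the N − B
- c = those PCS at baseline and again afterwards

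As written: (a + c) / (N − B). With matched sets: a / (N − B). Excess: c / (N − B), which is never negative.

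Write b = B/N for baseline prevalence and r = c/B for recurrence. The excess is then b × r / (1 − b). It does not depend on N, so it is the same formula in both arms.

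**Inputs.** The illustration uses N = 500, the planned atogepant arm (700 × 5/7 = 500, Protocol 4.1). Baseline prevalence, recurrence and new incidence are assumptions, because the documents give none of them.

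| b | r | New incidence | N − B | a | c | As written | Matched |
|---|---|---|---|---|---|---|---|
| 0% | any | 2% | 500 | 10 | 0 | 2.00% | 2.00% |
| 1% | 50% | 2% | 495 | 9.9 | 2.5 | 2.51% | 2.00% |
| 2% | 50% | 3% | 490 | 14.7 | 5 | 4.02% | 3.00% |
| 2% | 80% | 2% | 490 | 9.8 | 8 | 3.63% | 2.00% |
| 5% | 60% | 5% | 475 | 23.75 | 15 | 8.16% | 5.00% |
| 5% | 80% | 2% | 475 | 9.5 | 20 | 6.21% | 2.00% |
| 10% | 60% | 5% | 450 | 22.5 | 30 | 11.67% | 5.00% |

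**Range of the excess.** For b from 1% to 5% and r from 50% to 100%:

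- lowest: 0.01 × 0.5 / 0.99 = 0.51 points
- highest: 0.05 × 1.0 / 0.95 = 5.26 points

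**Effect of a baseline imbalance.** Assume 3% true new incidence and 60% recurrence in both arms, with baseline PCS of 2% in one arm and 5% in the other.

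- First arm: 3% + 0.02 × 0.6 / 0.98 = 3% + 1.22% = 4.22%
- Second arm: 3% + 0.05 × 0.6 / 0.95 = 3% + 3.16% = 6.16%

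The table would show a difference of about 1.9 points where there is none.

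**Parameters with a change criterion.** Their denominator needs only an available baseline, and a change cannot be computed without one. The mismatch does not arise there.

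**The case against.** The strongest defence is that the numerator sentence is merely elliptical. It follows directly on a sentence fixing the group to which the percentages relate, and a programmer would normally count cases within that group. SAP Section 4 also says that table specifications are held in a separate document, which may state the set correctly. This reading is possible, but SAP 11.2 and 11.4 spell out the condition in the same position, so its absence in 11.3 invites literal coding. Nothing in the documents supplied restores it.

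Several points about size do stand:

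- The criteria in Table 11-3 are not shown, so it is not known which parameters are affected. The 10% prevalence row has no support in the documents and only shows how the formula behaves.
- Exclusion criterion 12 (Protocol 4.4) removes participants with sitting systolic pressure above 160 mm Hg or diastolic above 100 mm Hg at Visit 1 or 2. That limits baseline PCS for high sitting blood pressure, but not for pulse or for low, standing or orthostatic values.
- Under randomization the inflation is equal in expectation across arms, so it adds no expected difference. It still misstates both levels, and chance imbalance remains.
- The table is descriptive. Summaries of values and changes, and a listing of PCS cases, accompany it. They let a reader trace the cases but do not correct the percentage.
- A result above 100% is possible only in theory. Even with b = 10% and full recurrence, the excess is 0.10 / 0.90 = 11.1 points, so new incidence would have to exceed 88.9%.

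**Conclusion.** The concern holds. For parameters with only an observed value criterion, SAP 11.3 as written divides by a group that does not contain everyone counted in the numerator. The direction is certain: the percentage can be overstated and never understated. Only the size is uncertain. The excess is 0.51 to 5.26 percentage points if 1% to 5% of participants are PCS at baseline and 50% to 100% of them are PCS again. It is zero if every participant counted as PCS after baseline had a non-PCS baseline value. Sample size and hypothesis tests are unaffected. What is affected is a by-arm safety percentage in a study whose stated objective is safety.

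**What to change.** Replace the numerator sentence in SAP 11.3 with wording to this effect: *for parameters with only an observed value criterion, count participants whose baseline value is available and not PCS and who have one or more PCS values after baseline; for all other parameters, count participants with an available baseline value and one or more PCS values after baseline.* Check that the separate table specifications say the same.

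This brings 11.3 into line with 11.2 and 11.4 and also removes participants without a baseline value from the numerator. The cost is one SAP sentence. It needs no new data, changes nothing in study conduct, and the supportive listing can still show participants who were PCS both before and after the first dose.

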11.4 Electrocardiograms

[figure not shown]
Descriptive statistics for ECG parameters (ie, heart rate, PR interval, QRS interval, RR interval, QT interval, and QTc interval) at baseline, postbaseline, and changes from baseline values at each postbaseline timepoint will be presented by treatment group.

ECG parameter values are considered PCS if ECG values meet either the actual value or change from baseline PCS high criteria listed in Table 11-4. The number and percentage of participants with PCS postbaseline values will be tabulated by treatment group. The percentages will be calculated relative to the number of participants with an available non-PCS baseline value and at least 1 postbaseline assessment. The numerator will be the total number of participants with an available non-PCS baseline value and at least 1 PCS postbaseline ECG value during the study. A supportive listing of participants with PCS postbaseline values will be provided. A listing of all AEs for participants with PCS ECG values will also be provided.

Table 11-4 Criteria for Potentially Clinically Significant Electrocardiograms

To evaluate ECG postbaseline values of clinical interest, the number and percentage of participants with post-treatment QTcF > 450 msec, > 480 msec, and > 500 msec will be tabulated by treatment group.

The number and percentage of participants with an increase > 30 msec but \le 60 msec, and with an increase > 60 msec in QTcF will be tabulated. Participants will be counted only once for the most severe category. A supportive listing of participants with postbaseline QTcF increases > 30 msec will be provided, including the PID number, study center, and all QTc values (including changes from baseline). A listing of all AEs for participants with postbaseline QTcF increases > 30 msec will also be provided.

A shift table from baseline to the end of open-label treatment period in the investigator's overall interpretation of the ECG will be presented by treatment group for the following categories: normal; abnormal, not clinically significant; abnormal, clinically significant. A tabular display of participants with postbaseline clinically significant ECG abnormalities according to the investigator's overall interpretation will be provided.

[figure not shown]

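### For any ECG parameter with both an actual-value and a change-from-baseline PCS limit, the by-arm PCS rate as written leaves out participants whose baseline already exceeds the actual-value limit, even when they newly meet the change limit

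*SAP*

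**What the plan says.** SAP 11.4 treats ECG values as PCS if they "meet either the actual value or change from baseline PCS high criteria listed in Table 11-4". Either limit alone is enough. The result is a by-arm table: "The number and percentage of participants with PCS postbaseline values will be tabulated by treatment group". For its denominator the SAP says: "The percentages will be calculated relative to the number of participants with an available non-PCS baseline value and at least 1 postbaseline assessment". The numerator is the number of "participants with an available non-PCS baseline value and at least 1 PCS postbaseline ECG value during the study". No exception is made for values that are PCS through the change limit.

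SAP 11.3 words the matching rule for vital signs differently. Its denominator is participants with "available baseline or non-PCS baseline (for parameters with only the observed value criterion) values and at least 1 postbaseline assessment". There the non-PCS-baseline condition is confined to parameters that have only an observed-value limit.

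SAP 11.4 also plans other ECG outputs, none with a stated baseline exclusion:

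- descriptive changes from baseline, by arm;
- counts of QTcF above 450, 480 and 500 msec, by arm;
- counts of QTcF increases of more than 30 and up to 60 msec, and of those "with an increase > 60 msec in QTcF will be tabulated"; this sentence names no split by arm and no denominator;
- a by-arm shift table of the investigator's overall interpretation;
- listings of participants with PCS postbaseline values and of those with QTcF increases above 30 msec.

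**The concern.** A baseline value has no change from itself, so a baseline ECG can be PCS only through the actual-value limit. Conditioning on a non-PCS baseline makes sense for that limit: someone already above it cannot newly cross it. It does not make sense for the change limit, which the same participant can still newly meet during treatment. Applying one condition to both limits removes that participant from numerator and denominator alike.

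The study's objective is safety and tolerability, and Protocol 3.1 says the SOC arm is there to give comparative safety data. By-arm safety rates are therefore a main output. A participant who starts with a long interval and then has a further large increase is one whom a safety reader would expect to find in the by-arm count.

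**Working it through.** **The rule applied to one parameter that carries both limits**

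| Baseline against actual-value limit | On-treatment event | In the by-arm PCS table of SAP 11.4? | Would a change-limit row need this participant? |
|---|---|---|---|
| Below | Crosses the actual-value limit | Yes | Only if the change limit is also met |
| Below | Meets the change limit | Yes | Yes |
| Above | Stays above, change limit not met | No | Yes, in the denominator |
| Above | Meets the change limit | No | Yes, in both |

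The last two rows are the gap. It exists only for parameters with both limits. The contents of Table 11-4 are not visible in the public text, so which parameters these are cannot be checked.

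**Comparison with SAP 11.3.** Where a vital sign has both limits, a value must meet both to be PCS. A baseline value cannot meet a change limit, so it cannot be PCS, and SAP 11.3 asks only for an available baseline. For ECGs either limit suffices, so a baseline can be PCS and the unrestricted condition removes people. The PCS definitions differ, and so do the consequences of the baseline condition.

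**Size.** The documents state no ECG rate, so there is no plan figure to reproduce. The only documented inputs are the planned arm sizes in Protocol 4.1: 700 × 5/7 = 500 atogepant and 700 × 2/7 = 200 SOC. These are randomized numbers; the ECG denominators will be somewhat smaller. The rest are assumptions:

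- b, the share with a PCS baseline on the parameter: 0.2% to 3%;
- r0, the rate of meeting the change limit among those with a non-PCS baseline: 1%;
- r1, the same rate among those with a PCS baseline: 0% to 20%.

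Rate as planned = r0 = 1.00%.

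Rate with everyone evaluable = (1 − b) × r0 + b × r1.

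| b | Dropped of 500 | Dropped of 200 | r1 = 0% | r1 = 1% | r1 = 5% | r1 = 20% |
|---|---|---|---|---|---|---|
| 0.2% | 1 | 0.4 | 0.998% | 1.000% | 1.008% | 1.038% |
| 1% | 5 | 2 | 0.990% | 1.000% | 1.040% | 1.190% |
| 3% | 15 | 6 | 0.970% | 1.000% | 1.120% | 1.570% |

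For example, at b = 3% and r1 = 20%: 0.97 × 1% + 0.03 × 20% = 0.97% + 0.60% = 1.57%. Events left out = N × b × r1, at most 500 × 0.03 × 0.20 = 3.0 (atogepant) and 200 × 0.03 × 0.20 = 1.2 (SOC). If r1 equals r0 the rate does not move, and if r1 is below r0 the planned rate is slightly too high. If b is zero nothing is lost.

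**The case against.** The strongest reply is that the gap may not exist in practice. If no parameter in Table 11-4 has both limits, or if the programmed tables show each limit in its own row and apply the condition per limit, nobody is excluded for the change limit. SAP 4 places table specifications in a separate document, so this is possible. It does not settle the matter, because SAP 11.4 states one condition for the whole PCS definition and should say so if it means something narrower.

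Four stronger readings are tempting, and the documents do not support them.

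- *Anyone with any PCS baseline ECG is dropped from the whole table.* PCS status is defined for parameter values, and SAP 11 sets baseline per safety parameter. The natural reading is that a participant with a high baseline on one parameter still counts for the others.
- *SAP 11.3 and 11.4 contradict each other.* They cover different measurements with different PCS definitions. This is an inconsistency in approach.
- *A further QTcF rise from a high baseline is visible only in a listing.* The QTcF increase categories are a number-and-percentage table with no baseline exclusion, and the by-arm change summaries include the maximum. The missing mention of arms in that one sentence may be a drafting slip. What stands is narrower. The increase table lacks a stated split and denominator. The counts above 450, 480 and 500 msec include people already above those values whether or not they rose. A parameter other than QTcF with both limits has no separate count of increases.
- *Up to about a quarter of atogepant change-limit events are missed.* With b = 3% and r1 = 10%, 500 × 0.03 × 0.10 = 1.5 events are left out against 500 × 0.97 × 0.01 = 4.85 counted, and 1.5/(1.5 + 4.85) = 23.6%. That needs a tenfold event rate in those dropped, for which the documents give no basis. Regression to the mean points the other way, and the Protocol Summary excludes clinically significant cardiovascular disease, which plausibly keeps b low.

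**Conclusion.** The point holds in a limited form. As literally written, SAP 11.4 leaves a participant above the actual-value limit at baseline out of the by-arm PCS rate for that parameter, including for a change limit that the participant newly meets. This rests on at least one ECG parameter carrying both limits, which cannot be verified. For QTcF the separate increase table largely covers the gap, subject to being shown by arm.

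The size is unknown and probably small. Under the assumed ranges the rate moves by −0.03 to +0.57 percentage points (0.97% to 1.57% against 1.00%), with no more than about 3 atogepant and 1.2 SOC events left out. It should not be described as a demonstrated downward bias: the direction depends on whether participants with a high baseline meet the change limit more or less often than the others. The planned safety summaries in view are descriptive, so no test or decision rule turns on it. It is a worthwhile correction of low priority.

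**What to change.** In SAP 11.4:

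1. Apply the non-PCS-baseline condition only to the actual-value limit.
2. For the change-from-baseline limit, use all participants with an available baseline and at least one postbaseline ECG for that parameter, as numerator base and denominator. This follows the reasoning of SAP 11.3.
3. Show the two limits as separate rows by treatment arm.
4. Present the QTcF increase categories by treatment arm with the denominator in item 2.

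The cost is a few sentences in the SAP and minor programming. No new data are needed.

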# 5.3 Methods for Masking/Blinding

This is an open-label study.

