## 6.4.6 Electrocardiograms

A 12-lead ECG will be performed at the visits outlined in Table 1. All ECGs should be performed after the participant has been supine for at least 5 minutes. All ECGs performed will be saved as a source document. ECGs will be transmitted electronically to the central ECG laboratory for analysis according to the instructions provided by the laboratory to be centrally read by a cardiologist. The overall interpretation of the clinical significance of the ECG will be determined by the investigator and recorded in the participant's eCRF.

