#### Amendment Summary

This amendment includes changes made to Protocol 3101-302-002 Amendment 1 dated 14 March 2019.

To eliminate immediate potential hazards to participants and study staff due to the COVID-19 pandemic while ensuring participant safety and maintaining data integrity, the protocol was updated to allow investigators/appropriately designated study staff to perform Visit 14, Visit 15/ET, and Visit 16/SFU as remote study visits (eg, conducted via phone, video conference), as follows:

- Investigators/appropriately designated study staff are allowed to perform Visit 14 and Visit 15/ET as remote study visits.
- Investigators/appropriately designated study staff should conduct Visit 16/SFU Visit remotely for all participants in all cases.
- Safety assessments to be completed at remote study visits include assessment of AEs, concomitant medications, pregnancy test results review, and the C-SSRS.

The protocol also was amended to:

- Update the definition of safety population.
- Remove subgroup analysis by prior treatment failure with oral medications.

The table below provides details related to content changes that were made in the protocol, and a brief rationale for these changes. Minor editorial and document formatting revisions have not been summarized.

Section	Revision	Rationale
Table 1 Schedule of Visits	Investigators/appropriately designated study staff	To eliminate immediate
and Procedures;	are allowed to perform Visit 14 and Visit 15/ET	potential hazards to
8.4.2.2 Visits 3 to 14	Visit as remote study visits (eg, conducted via	participants and study
(Week 4 to 48)	phone, video conference).	staff due to the
Section 8.4.2.3	Investigators/appropriately designated study staff will perform Visit 16/SFU Visit as a remote study	COVID-19 pandemic
Visit 15/Early Termination	visit (eg, conducted via phone, video conference).	while ensuring
(Week 52)	Table 1 footnotes t, u, v, w were added for clarity.	participant safety and
8.4.3.1 Visit 16/End of	Safety assessments to be completed at remote study	maintaining data
Study (Week 56)	visits include assessment of AEs, concomitant	integrity
Conducted During	medications, pregnancy test results review, and the C-SSRS	
In-Person Visit (Prior to	Physical examination, ECG, vital sign	
the COVID-19 Pandemic)	measurements, clinical laboratory determinations,	
Section 8.4.3.1.1 Visit 16/	and PRO measures will not be performed at the	
End of Study (Week 56)	remotely conducted visits.	

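### The by-arm table of investigator ECG interpretation looks only at end of treatment, so abnormal ratings that resolve earlier are not counted by arm

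*SAP*

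**What the plan says.** SAP 11.4 plans "A shift table from baseline to the end of open-label treatment period in the investigator's overall interpretation of the ECG", which "will be presented by treatment group for the following categories: normal; abnormal, not clinically significant; abnormal, clinically significant". The next sentence adds a listing-type output without that time limit: "A tabular display of participants with postbaseline clinically significant ECG abnormalities according to the investigator's overall interpretation will be provided". No count per arm is stated for that display, and it covers only the clinically significant category.

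The rating is a judgement by someone who knows the treatment. Protocol 5.3 says "This is an open-label study", and Protocol 6.4.6 says "The overall interpretation of the clinical significance of the ECG will be determined by the investigator and recorded in the participant's eCRF". The same protocol section has ECGs "transmitted electronically to the central ECG laboratory for analysis according to the instructions provided by the laboratory to be centrally read by a cardiologist", but the visible SAP plans no categorical table from that reading.

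The rest of SAP 11.4 is not tied to the end of treatment. By arm, it gives ECG parameters at each postbaseline timepoint, participants with at least one potentially clinically significant (PCS) postbaseline value, and participants with QTcF above 450, 480 and 500 msec. It also tabulates QTcF increases of more than 30 up to 60 msec and of more than 60 msec, counting each participant once in the most severe category.

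**The concern.** Protocol 3.1 says the SOC arm exists to provide comparative safety data over 52 weeks. For findings that are not expressed as heart rate or an interval, the overall interpretation is the only route into a by-arm ECG summary in SAP 11.4. That summary compares two time points, so whatever happens on ECGs between them is not compared between arms. A reader of the study report could not tell from the table whether transient abnormal ratings were more common on atogepant or on SOC medication. For the clinically significant ones, the reader would have to count rows in a display. For the others there is nothing to count.

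The time point also has a practical weakness. The Amendment 2 summary (Protocol 12.6) says "Investigators/appropriately designated study staff are allowed to perform Visit 14 and Visit 15/ET as remote study visits", and lists ECG among the assessments not performed remotely.

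A second, smaller issue is who makes the rating. If investigators who know the arm apply a lower threshold in one arm, the difference appears in this table as a treatment difference.

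**Working it through.** **Plan's own figures.** The documents give no expected rate, target or power for this table. The arm sizes reproduce: 700 × 5/7 = 500 and 700 × 2/7 = 200.

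**Where an abnormal rating goes, from SAP 11.4:**

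| Investigator rating | Present at end of treatment | Resolved before end of treatment |
|---|---|---|
| Abnormal, clinically significant | By-arm shift table and participant display | Participant display only, no stated count by arm |
| Abnormal, not clinically significant | By-arm shift table | No visible summary |
| Numeric PCS or QTcF criterion met | Any-visit tables | Any-visit tables |

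The gap is the right-hand column of the first two rows.

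**Counting convention elsewhere.** SAP 11.4 counts a PCS value at any time in the study and places QTcF increases in the most severe category. SAP 11.5 reports the most severe ideation and behaviour over the treatment period. The interpretation shift is the exception.

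**Illustration 1: end-only against worst value (assumed inputs).** The ECG schedule is not visible, so K, the number of postbaseline ECGs, is assumed to be 3 to 5. The chance p of an abnormal rating at any one ECG is assumed to be 1%.
- End-only: p = 1.0%.
- Worst of K, independent between ECGs: 1 − (1 − p)^K. For K = 3, 1 − 0.99³ = 3.0%. For K = 5, 1 − 0.99⁵ = 4.9%.
- Worst of K, fully persistent (the same participants abnormal every time): 1.0%, so nothing is lost.

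The answer depends on persistence and runs from no loss to the independent figures.

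**Illustration 2: share missed when an abnormality lasts for one ECG only (assumed).** If it is equally likely to fall on any of K on-treatment ECGs, the last one shows 1/K and the end-only table misses 1 − 1/K: 50% for K = 2, 67% for K = 3 and 75% for K = 4.

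**Illustration 3: unequal thresholds (assumed).** With the same true abnormal rate p in both arms and extra false calls q in one arm, the apparent difference is (1 − p) × q. For p = 10% and q = 1% it is 0.90 × 0.01 = 0.9 percentage points. For p = 2% and q = 5% it is 0.98 × 0.05 = 4.9 points. Nothing in the documents indicates that thresholds do differ. This shows only how such a difference would carry into the table.

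**The case against.** The strongest reply is that SAP 11.4 already covers transient ECG abnormalities. Numeric abnormalities at any postbaseline visit are tabulated by arm without using the investigator's rating, and clinically significant ratings at any postbaseline visit are displayed. This stands, and a reader who infers that the ECG plan as a whole misses transient findings would be wrong. What remains is the by-arm count for transient clinically significant ratings and any summary at all for transient lesser ones. The SAP introduction places table specifications in a separate document, which may supply that count, but the SAP text does not require it.

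A reader might also take the sample-size section's retention figures (0.60 × 0.65 = 39%, or 195 of 500 on atogepant) as the share with an end-of-treatment ECG. The documents do not support that. The figure is expected 12-month completion. Week 52 and early termination share Visit 15/ET, and Protocol 8.8 asks that all who stop early be seen for those evaluations. Likewise, the effect of remote visits cannot be sized. The rule that selects the end-of-treatment ECG is not visible, and SAP 18.2 counts ECGs missed because of COVID-19 separately.

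A third tempting step is to replace the investigator's rating with the central one as a bias-free substitute already in hand. Protocol 6.4.6 does not say that the cardiologist is unaware of arm, that the reading gives a normal/abnormal category, or that the investigator rates without seeing it. It assigns clinical significance to the investigator, and the SAP follows that assignment. Requiring a new category from the central reader could mean re-reading ECGs already read.

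Finally, the visible safety analyses are descriptive, and no stated decision rests on this table. That limits the weight of the point but does not remove it.

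**Conclusion.** The point holds in a narrow form. The only visible by-arm summary of overall ECG interpretation is confined to baseline and end of treatment. Transient clinically significant ratings therefore have no stated by-arm count, and transient lesser ratings have no visible summary. The numeric ECG tables are sound on this issue.

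The size cannot be derived from the documents. The contrast of 1.0% with 3.0% to 4.9% is an illustration that assumes a 1% rate per ECG, independence and 3 to 5 ECGs; with fully persistent abnormalities the contrast vanishes. Assessment bias from knowledge of arm is possible because the study is open-label and the rating is subjective, but it is not shown. This is a low-cost improvement to a descriptive table, not a defect that undermines the safety conclusions.

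**What to change.** In SAP 11.4, add a by-arm shift table from baseline to the worst postbaseline investigator interpretation, ordered normal, abnormal not clinically significant, abnormal clinically significant. It uses ratings already recorded in the eCRF. Keep the end-of-treatment shift and the participant display. State which postbaseline ECGs count, including unscheduled ones.

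Also state whether the central cardiologist's reading gives an overall category and whether it is made without knowledge of arm. If both are so, present the same worst-postbaseline table from that reading as supportive. Do not replace the investigator's table.

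The cost is SAP wording and one or two descriptive tables, with no new ECGs. There are two downsides. A worst-value summary shows higher abnormality percentages in both arms. It also depends on how many ECGs each participant has: under the assumptions of illustration 1, 5 ECGs in one arm against 3 in the other would give 4.9% against 3.0% with no true difference. Showing the number of postbaseline ECGs per participant by arm beside the table lets the reader judge this.
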